#### 10.3.6. Optional Observational Substudy

Subjects who complete the study will be offered an opportunity to participate in an observational substudy at the Post Attack 3 visit. The subjects will provide consent and will record details of all HAE attacks into an HAE diary, dispensed at the Post-Attack 3 visit that occur for approximately 12 weeks.

The following assessments will be performed after the Post-Attack 3 visit:

- Week 4, 8, 12 of the observational period: phone call to discuss completion of the HAE attack diary, collection of completed diaries (in person or via mail) and whether additional diaries are needed. In addition, AEs assessed as possibly, probably or definitely related to study drug will also be collected
- Week 4, 8, 12: review of completed HAE diaries for correctness/completeness

#### 11. ASSESSMENTS

The schedule of procedures/assessments to be conducted is outlined by study day in Table 4 with details on the conduct of the procedures/assessments provided below.

# 11.1. Investigator-Completed Assessments

Demographic information, including year of birth, sex, race or ethnicity, and medical history will be captured for each subject participating in the study at the Screening visit. Medical history and review of inclusion and exclusion criteria will also be rechecked at the Baseline visit.

Contraceptive methods enabling eligibility will be captured in source documentation at the screening visit.

## 11.1.1. HAE Medical and Medication History

An HAE medical history questionnaire provided by the Sponsor will be completed at Screening. All questions should be completed by the Investigator (or designee) from historical source documentation when available, with subject input as necessary to complete the remaining questions. The completed HAE Medical History Questionnaire will be considered a source document and must be entered in the eCRF in full to enable Sponsor confirmation of the subject and randomization (see Section 9.3.2).

# 11.1.2. Physical Examination

A full physical examination should be conducted at Screening and Baseline. All subsequent physical examinations may be targeted (i.e., symptom-driven). Genitourinary and breast examinations may be omitted when not required by normal site practice.

#### 11.1.3. Weight/Body Mass Index

For determination of height and weight, subjects should be dressed, without shoes. Body mass index should be calculated using the following formula:

$$BMI = weight (kg)/height (m)^2$$

#### 11.1.4. 12-lead Electrocardiograms

A standard bedside 12-lead ECG machine that calculates heart rate and measures the PR, QRS, QT, RR, and QTc (QTcF) intervals will be utilized. Prior to obtaining an ECG, subjects must rest quietly in a supine position for at least 10 minutes.

Qualified site personnel should review the ECGs and automated findings in real-time for gross abnormalities and interval measurements of concern (absolute readings and for postdose ECGs, change from baseline). For all ECGs, the clinical interpretation of the ECG should be recorded directly on a hard copy of the ECGs. Copies of the ECGs may be requested by the Sponsor.

All ECGs will be captured as single assessments.

An ECG should be repeated during the clinic visit if possible for a change from baseline in QTcF > 60 msec or a QTcF interval > 500 msec for confirmation of the change.

#### 11.1.5. Vital Signs

Blood pressure (systolic and diastolic) and heart rate should be taken after the subject has rested in the supine position for at least 5 minutes. Blood pressure measurements must be obtained with an appropriate cuff size and with the subject's arm supported at the level of the heart. It is acceptable to obtain a pulse rate from the blood pressure or ECG machine.

Temperature will also be obtained at all visits.

#### 11.1.6. Clinical Laboratory Assessments

Blood and urine samples will be obtained per the schedule of events. Individual laboratory tests to be performed are provided in Table 6. Laboratory samples should be obtained in the fasted state.

Laboratory samples will be routinely analysed by a centralized laboratory with the exception of urine pregnancy tests which will be assessed locally at the site. A laboratory reference manual will be provided to the site detailing laboratory kit contents reordering instructions, sample collection, handling, storage and shipment. Results from the laboratory values should be reviewed as received by the Investigator. Evidence of this review should be provided in the source records and may include printing of the laboratory reports with a signature attesting to a review. For out-of-range lab findings, the interpretation of clinically significant or not clinically significant should be denoted in the source records. Clinically significant laboratory findings in the opinion of the Investigator should be recorded as an AE and handled as described in Section 12.1.

**Table 6.** Clinical Laboratory Evaluations

Chemistry	Hematology

 
Albumin
 
Alkaline phosphatase (ALP)
 
Alanine aminotransferase (ALT)
 
Aspartate aminotransferase (AST)
 
Bilirubin (total and direct)
 
Blood glucose (fasting)
 
Blood urea nitrogen (BUN)
 
Electrolytes (calcium, sodium, potassium, chloride, phosphorus)
 
Creatine kinase
 
	
 
Hemoglobin
 
Hematocrit
 
Erythrocytes
 
MCH
 
MCHC
 
MCV
 
White blood cell count, with differential (lymphocytes, monocytes, neutrophils, eosinophils, and basophils)
 
Platelets
 

 
Creatinine and calculated creatinine clearance
 
Gamma-glutamyltransferase (GGT)
 
Lactate dehydrogenase (LDH)
 
Total serum protein
 
Uric acid
 
Amylase
 
*reflex to lipase for amylase > 2x ULN
 
	

	Pregnancy Test			
	Serum (screening) and urine (other scheduled visits) βHCG for women of childbearing potential only			
	Drug screen			
	Amphetamines			
Urinalysis	Barbiturates			
· ·	Benzodiazepines			
Specific gravity	Cocaine			
Blood     Bilirubin	Opiates			
Glucose	Methamphetamine			
Leukocytes	• Ecstasy			
Ketones				
Nitrates	Additional Tests			
• pH	Follicle-stimulating hormone (FSH; screening)			
Protein	for women postmenopausal ≤ 2 years			
Urobilinogen	Hepatitis B surface antigen, Hepatitis C			
Microalbumin to creatinine ratio	antibody, HIV antibody (screening)			
Microscopy if dipstick is abnormal	Troponin I Troponin T			
Coagulation	• CK-MB			
Prothrombin time (PT) and international	C1 INH function			
normalized ratio (INR)	• C4			
Activated partial thromboplastin time (aPTT)	C1 INH antigen			
· · · · · · · · · · · · · · · · · · ·	• C3			

Creatinine clearance ( $CL_{cr}$ ) will be calculated using the Cockcroft-Gault formula and actual body weight (ABW):

$$CL_{cr}$$
 (mL/min) =  $\underline{(140 - age \text{ in years}) \times ABW \text{ (kg)}}$  (× 0.85 for females)  
 $72 \times \text{serum creatinine (in mg/dL)}$ 

# 11.1.7. Screening for Human Immunodeficiency Virus, Hepatitis B, and Hepatitis Serology

Blood samples will be collected at screening for serologic testing for evidence of HIV, chronic hepatitis B, and hepatitis C infection. Subjects with a positive Hepatitis C antibody but have no evidence for HCV RNA upon reflex testing are eligible for study participation.

#### 11.1.8. Pregnancy Testing

Follicle stimulating hormone will be measured at Screening in women declaring themselves postmenopausal  $\leq 2$  years to establish childbearing status. At Screening, a serum pregnancy test should also be drawn in the event a woman subject postmenopausal  $\leq 2$  years is found to be of childbearing potential.

A serum pregnancy test will be administered to women of childbearing potential or who are postmenopausal  $\leq 2$  years at Screening; all other pregnancy tests performed during the study may be urine pregnancy tests (for women of childbearing potential only). A serum pregnancy test should immediately be drawn and sent for analysis for any positive urine pregnancy test.

#### **11.1.9. C1 INH Testing**

C1 INH functional level and C4 will be measured at screening to establish the laboratory diagnosis of HAE Type 1 or 2. These tests should be drawn at least 3 days after a previous dose of C1 INH.

Should C4 be normal, as is the case in a small percentage of subjects with HAE, C4 may be drawn during an attack or the SERPING-1 gene may be analyzed and the subject confirmed eligible if a known mutation associated with HAE Types 1 or 2 is identified.

C1 INH antigen level will be drawn for demography on enrolled subjects at the Baseline visit.

#### 11.1.10. Other Laboratory Assessments

Troponin I, Troponin T and CK-MB will be measured in this study at all time points beginning at Baseline (i.e., Post-Attack 1, 2, and 3 clinic visits and early termination visit [if applicable]). C3 levels will be taken at Baseline on all subjects and will only be drawn on-study if required for AE assessment (see Section 11.1.11).

#### 11.1.11. Rash Assessment

Because of the potential for a study drug-related rash (see Section 5.3), all sites are required to have the ability to obtain high resolution photographs and obtain an appropriate skin biopsy. These can be performed by experienced site physicians or a dermatologist on retainer for this study.

Subjects should be medically evaluated within 24 to 36 hours of awareness of any treatment-emergent rash, regardless of grade or causality, and the site must inform the Sponsor medical monitor at the time the rash is diagnosed via the Event of Special Interest Form (Section 12.1.5.1). In the event the site is notified of a rash on the weekend or holiday, the medical evaluation and Sponsor notification can be performed on the next working day.

The following assessments must be completed for all subjects with a rash, regardless of causality, as soon as logistically possible:

• Full dermatological exam to include the anatomical location(s) of the rash, vital signs, and mucosal examination. The notes documenting the examination should include detailed description of the rash, presence or absence of blistering and if present, its extent and presence or absence of mucosal involvement and if present, its extent and any other associated abnormal physical findings.

- High resolution photographs taken to provide both detail regarding the rash and details regarding the extent of the rash. Cameras must be able to provide clear images taken in close proximity to the skin. The picture should include a ruler (centimeter) for scale. Every attempt to protect subject anonymity should be made.
- All detailed clinical information regarding the rash, examination, clinical and laboratory assessments, treatment and interpretation of the event needs to be reported on an SAE/Event of Special Interest Report form as per Section 12.1.5.1.

The following assessments must be completed for all subjects with a rash assessed as possibly, probably, or definitely related to study drug by the Investigator as soon as logistically possible:

- Blood taken for clinical chemistry, hematology including differential, and C3 level. Table 6 outlines the clinical chemistry and hematology analytes to be assessed.
- Urine sent to local laboratory for urine eosinophils (if evaluation is available locally)
- Subjects will also be requested to donate a blood sample for peripheral blood mononuclear cells (PBMCs) for analysis of possible drug-specific immune responses and possible drug-responsive T-cells. This sample should be obtained preferably 1-3 months after occurrence of the rash. Information on PBMC collection, processing and shipment will be communicated to sites prior to sample collection.

# 11.2. Subject-Completed Assessments

#### 11.2.1. Treatment Satisfaction Questionnaire

To assess treatment satisfaction of the medication a TSQM will be administered once at Baseline and at each clinic visit following treatment of an acute attack with study drug. At Baseline, the TSQM will be completed in reference to the subject's currently used acute attack medication prescribed/authorized by their HAE treater; at each subsequent study visit, the TSQM will be completed in reference to the attack previously treated with study drug

For all subject-completed forms, clinic staff should ensure the subject reads the instructions and completes the questionnaires in full prior to filing in the source documentation.

#### 11.2.2. HAE Attack Diaries and Phone Calls

## 11.2.2.1. Screening through Post-Attack 3 Visit

The Sponsor will supply an attack diary for subject documentation of one HAE attack occurring during the screening period and for each of 3 study-drug treated attacks. To ensure compliance with on-study requirements in treating an appropriate attack with study drug after the Baseline visit, subjects will be required to complete timed attack details of at least 1 HAE attack during the screening period after approval of the on-call Investigator (or designee). Subjects will also be required to complete the details of three HAE attacks that are treated with study drug, each after approval from the on-call Investigator (or designee).

All attacks for which acute attack diaries are completed by the subject will be included in the eCRF.

Apart from the principal Investigator at each clinical site, the Sponsor will approve on-call study Investigators (or designees). Approval will be based upon demonstration that the proposed on-call Investigator (or designee) ordinarily has oversight of the care of HAE patients.

The diaries will be composed of a questionnaire and 3-component VAS on a 100 mm scale for abdominal pain, cutaneous pain, and cutaneous swelling. The questionnaire includes queries about symptom location, severity/limitation of activities and a global assessment that qualitatively compares HAE symptomatology against that experienced prior to study drug intake. The diaries will include questions/VAS to be completed prior to study drug administration and 1, 2, 3, 4, approximately 8 and at 24 hours post study drug intake (or post call for a screening attack). All medications used from the time of symptom onset through 24 hours postdose will also be captured in the diary, including standard of care treatment for acute attacks and any symptomatic treatments such as analgesics.

At the Screening, Baseline, and Post-Attack 1 and Post-Attack 2 visits, attack diaries will be dispensed and the subject will be instructed on completing the diary (written instructions may also be provided). In addition, subjects will be informed of what is expected regarding attacks likely to be approved for study drug treatment by the Investigator and also administration of standard of care rescue medication on a continuing basis.

At the Baseline and Post-Attack 1, 2, and 3 visits, sites must collect and review the diary for completeness and plausibility; any re-education required to ensure correct diary completion will be performed. Study staff are not permitted to make any entries into the diary regarding HAE attack information.

Diary instruction will include demonstration on how to properly complete the VAS, review of all questions for understanding, and those questions that allow more than one response. Subjects must be instructed to complete all questions unless medically prevented from doing so or the subject is sleeping after a treated attack, and the importance of completing the diary at the scheduled time points must be stressed.

Following the Baseline visit and prior to the Post-Attack 3 visit, subjects will be asked to record the start and stop time of all HAE attacks that occur and any standard of care administration.

#### 11.2.2.1.1. Documented Screening Attack

The documented screening attack is intended as a practice for on-study requirements in the identification, approval, and documentation of an HAE attack treated with study drug. As such, the steps required in identifying, approving and documenting the attack should be as close to as would be expected or required after the Baseline visit. All steps must take place (initial call for HAE symptom review, HAE attack diary documentation, return call) to assess a subject's understanding and compliance with the study requirements. The Investigator (or designee) may request that the subject complete more than one documented screening attack if he or she is not satisfied that the subject has demonstrated compliance with the procedures required for treating and documenting attacks.

At the first symptom of swelling or pain associated with at least one HAE attack occurring during the Screening period, the subject will phone their on-call study Investigator (or designee) who will review the subject's symptoms by phone. It is preferable that the subject call the Investigator within one hour of symptoms and that the attack is one that is protocol-qualified

on-study (see Section 11.2.2.1.2). Subjects will not be asked to avoid standard of care attack treatment for four hours from the phone call.

During the documented Screening HAE attack, subjects will record the occurrence and details of the HAE attack in the diary immediately after the call to the Investigator as well as any medications used since the onset of symptoms. Subjects will fill out the diary questionnaire and a 3-component VAS at 1, 2, 3, 4, approximately 8 and at 24 hours after the phone call. Any questions regarding study drug administration may be left blank.

The subject will be asked to phone the on-call study Investigator (or designee) at least 4 hours after the phone call to review diary completion. The on-call study Investigator will call the subject if they have not heard from the subject within 5 hours of their initial phone call.

An exception to the requirement of a phone call follow-up at 4 hours may be made if the 4 hour timepoint occurs during the typical period of sleep and the subject is asleep at 4 hours post-study medication. In this case, the subject will be required to call the on-call Investigator (or designee) upon waking. The on-call Investigator (or designee) and subject may agree at the initial attack approval phone call that the subject will try to rest to avoid an Investigator call 5 hours later. For subjects who were sleeping during diary-required timepoints after the phone call, only the 4 hour timepoint in the diary questionnaire is required to be completed at the time they awake and any medications taken.

The on-call Investigator (or designee) will document the details of both calls.

# 11.2.2.1.2. On-Study Attacks

After the Baseline and Attack 1 and 2 visits, the subject will phone their on-call study Investigator (or designee) at the first symptom of swelling or pain associated with a potentially protocol-qualified HAE attack. The Investigator (or designee) will review the subject's symptoms and confirm that they constitute an acute attack that qualifies for treatment with study drug, including ensuring that the subject is in an environment that he/she deems suitable for completion of the timed diary.

Protocol-qualified attacks approved for treatment must meet all of the following:

- have pain and/or swelling associated with an HAE attack reported as a symptom
- subject has contacted Investigator within approximately 1 hour of onset time of HAE pain and/or swelling
- not involve HAE pain or swelling in the throat or mouth. Such attacks should be treated using the subject's standard of care acute attack treatment (e.g., C1 INH, icatibant).
- not be an abdominal attack that has already resulted in vomiting. Such attacks should be treated using the subject's standard of care acute attack treatment (e.g., C1 INH, icatibant).
- have an identifiable onset time, with the exception that abdominal attacks with an onset during sleep may be permitted for study drug treatment. Onset time for approved abdominal attacks will be time the subject woke up with symptoms.

Peripheral attacks starting with an onset during sleep are not to be authorized for study drug treatment.

- occur during an HAE symptom-free period as follows:
  - o if the previous HAE attack was treated with a bradykinin B2 receptor antagonist (i.e. Firazyr) OR treated with human recombinant C1 INH (i.e. Ruconest) OR any non-targeted therapy (i.e. pain medication, anti-spasmodic, anti-emetic, tranexamic acid) OR was not treated with any medication: new attack can be treated with IMP if has been 48 hours since the complete resolution of all symptoms of the previous HAE attack AND the Investigator believes it is a new (de novo) attack.

OR

- o if the previous HAE attack was treated with plasma-derived purified C1 INH (i.e. Berinert or Cinryze) OR plasma preparation (fresh frozen or solvent detergent plasma): new attack can be treated with IMP if it has been 96 hours since the complete resolution of all symptoms of the previous HAE attack
- occur at least 96 hours after complete recovery from a procedure or injury
- occur at least 14 days from a previous dose of study drug

Following confirmation by the Investigator that an attack may be treated with study drug, subjects should reconstitute and take study drug almost immediately (within 5 minutes) following the approval phone call, with the goal for subjects to take study drug within or approximately one hour of the onset of symptoms. Subjects will be asked to avoid food for at least one hour after taking study drug and will be asked to withhold standard of care attack treatment for four hours from administration of study drug (see Section 9.2). If symptoms are progressing rapidly or if intraoral symptoms occur, subjects may treat the attack with their standard of care attack medication prior to 4 hours.

The subject will be asked to phone the on-call study Investigator (or designee) at least 4 hours after taking study medication (or earlier if they have any concerns over the course of their symptoms) to review their response to study drug and diary completion, unless they are sleeping. The on-call study Investigator will call the subject if they have not heard from the subject within 5 hours of their initial phone call. Subjects who did not require standard of care at 4 hours will be reminded at the telephone call by the Investigator that they may use standard of care at any time point at their own discretion if not experiencing improvement or who are experiencing progression of the HAE attack.

An exception to the requirement of a phone call follow-up at 4 hours may be made if the 4 hour timepoint occurs during the typical period of sleep and the subject is asleep at 4 hours post-study medication. In this case, the subject will be required to call the on-call Investigator (or designee) upon waking. The on-call Investigator (or designee) and subject may agree at the initial attack approval phone call that the subject will try to rest to avoid an Investigator call 5 hours later.

Subjects will record the occurrence and details of the HAE attack immediately prior to treating the approved HAE attack with study drug. Subjects will also fill out the diary questionnaire and a 3-component VAS at 1, 2, 3, 4, approximately 8 and at 24 hours after record of study drug

administration. All medications taken after study drug administration through 24 hours will also be captured. For subjects who were sleeping during these timepoints after administration of study drug, subjects are only required to fill out the 4 hour timepoint in the diary questionnaire and any medications taken at the time they awake.

The on-call Investigator will document the details of both calls involving approval of and follow-up after study drug treatment. If duplicate data is collected on this form and in the HAE diary, the HAE diary will always be source documentation. In the event that a diary field is empty when reviewed subsequently at the Post-Attack 1, 2, or 3 visit, the details of the Investigator form may serve as source documentation.

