- 4. The subject will call the on-call study Investigator (or designee) at least 4 hours after taking study medication (or earlier if they have any concerns over the course of their symptoms) to review their response to study drug and diary completion. The on-call study Investigator (or designee) will call the subject if they have not heard from the subject within 5 hours of their initial phone call. Subjects who did not require standard of care at 4 hours will be reminded at the telephone call, by the Investigator, that they may use standard of care at any time point at their own discretion if not experiencing improvement or if they are experiencing progression of the HAE attack. An exception to the requirement of a phone call follow-up at 4 hours may be made if the 4 hour timepoint occurs during the typical period of sleep and the subject is asleep at 4 hours post-study medication. In this case, the subject will be required to call the on-call Investigator (or designee) upon waking.

Subjects will complete a diary questionnaire and a 3-component VAS on a 100 mm scale for abdominal pain, cutaneous pain, and cutaneous swelling immediately prior to study drug administration and at 1, 2, 3, 4, approximately 8 and at 24 hours after study drug administration. Subjects sleeping during these timepoints (see #4 exception above) will be required to complete the diary questionnaire upon waking. Subjects will also be asked to track the start and stop times of any attacks not treated with study drug that occur after the baseline visit through the last study visit (Post-Attack 3 visit).

At each clinic visit following treatment of an attack with study drug, the diary will be reviewed. Any re-education required to ensure correct diary completion will be performed and safety assessments will be completed. At Post-Attack 1 and Post-Attack 2 clinic visits, the subject will be dispensed their next randomized dose of study drug and a new attack diary. Completed diaries will be collected at each visit to avoid subjects referencing back to previous attack entries.

Each subject will continue on study to treat 3 protocol-qualifying attacks with study drug. Clinic visits will be scheduled 10 to 14 days after each attack that is treated with study drug. Any additional attacks that occur in the intervening periods between study visits may be treated according to standard of care for the subject.

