## 7.2. Endpoints

# 7.2.1. Efficacy Endpoints

The efficacy endpoints of this study are as follows:

- Proportion of subject attacks with an improved or stable 3-symptom composite VAS score at 4 hours post-dose. The 3-symptom composite will be calculated as the average of the VAS scores for abdominal pain, skin pain, and skin swelling. A subject is considered improved or stable if the change from baseline (time of drug administration) in VAS is less than or equal to 0
- Proportion of subject attacks with a patient global assessment of improved or stable symptoms at 4 hours post-dose
- Proportion of subject attacks with no symptoms or mild symptoms of an HAE attack at 4 hours post-dose
- Proportion of subject attacks requiring standard of care attack treatment through 24 hours post-dose
- Time to use of standard of care acute attack treatment through 24 hours post-dose
- Time to stable or improved symptoms by composite VAS score through 24 hours post-dose
- Time to symptom relief (first documented time point when a subject experiences a 50% reduction in the 3-symptom composite VAS from the pretreatment composite score)
- Time to almost complete symptom relief (first documented time point when a subject records a VAS score < 10 mm in the 3-symptom composite VAS score)
- Time to initial symptom relief (time from ingestion of study medication to report that the worst symptoms of the attack are over)
- Time to complete symptom relief (time from ingestion of study medication to no HAE attack symptoms)

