# 13.3.3. Analysis of Efficacy Variables

As this is the first study of BCX7353 in the treatment of acute attacks, the analysis of attack resolution will be described in a number of ways which will be fully detailed in the SAP. The endpoint that may be utilized to first examine efficacy is the proportion of subject attacks with a stable or improved VAS at 4 hours postdose in the full analysis set. The number and proportion of subject attacks with a stable or improved VAS at 4 hours postdose will be summarized by treatment group. Attacks that require standard of care medication prior to the 4 hour time point will be considered as failure (i.e., not having a stable or improved VAS at 4 hours postdose). To assess treatment differences, a logistic mixed effect model including treatment, period and sequence as fixed effects, and subject within sequence as a random effect will be utilized. Other binary endpoints will be analyzed in a similar manner.

The 3-symptom composite VAS and its associated changes from baseline will be summarized for each attack by time point and treatment group. Treatment differences in the change from baseline values at each time point will be assessed with a mixed effect linear model with factors for treatment, period, sequence, and baseline value as fixed effects, and subject within sequence as a random effect. Analyses of other continuous variables will be analyzed in a similar manner.

The time to use of standard of care medication will be estimated using the method of Kaplan-Meier. For each attack, subjects who do not use standard of care medication will be censored at the end of the attack observation period (i.e., 24 hours). Treatment differences will be assessed using an appropriate proportional hazards model. Analyses of other type to event variables will be analyzed in a similar manner.

Location of attacks, duration of attacks, and number of acute HAE medications administered will be summarized for each treatment group.

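### A subject asleep at 4 hours completes the 4-hour diary entry on waking, with no latest time, so late readings can stand as 4-hour results

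*Protocol*

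**What the plan says.** **Endpoint.** The first efficacy endpoint in protocol 7.2.1 is "Proportion of subject attacks with an improved or stable 3-symptom composite VAS score at 4 hours post-dose", met when the change from baseline is zero or less. Sections 13.2 and 13.3.6 name it as the endpoint that may be tested at p < 0.001, from the point when 12 subjects have completed Part 1. Two more endpoints in 7.2.1 are also read at 4 hours: the patient global assessment, and having no or mild symptoms. None has a time window.

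**Diary.** Section 11.2.2.1 states: "The diaries will be composed of a questionnaire and 3-component VAS on a 100 mm scale". The severity and global-assessment items belong to the questionnaire part.

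**Sleep rule.** For subjects asleep at the scheduled times, section 11.2.2.1.2 says "subjects are only required to fill out the 4 hour timepoint in the diary questionnaire and any medications taken at the time they awake". Section 7.1.2 says such subjects "will be required to complete the diary questionnaire upon waking", without limiting this to the 4-hour entry. The subject and the investigator "may agree at the initial attack approval phone call that the subject will try to rest to avoid an Investigator call 5 hours later", so sleeping through 4 hours can be planned.

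**Rescue.** Section 13.3.3 says: "Attacks that require standard of care medication prior to the 4 hour time point will be considered as failure". After 4 hours, subjects whose attack is progressing or not improving are reminded that "they may use standard of care at any time point at their own discretion".

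**Analysis detail.** Section 13.3 leaves time points and missing data to a SAP. The SAP supplied is for study BCX7353-302, a prophylaxis trial, and has no 4-hour VAS endpoint.

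**The concern.** An entry made on waking is not a 4-hour measurement. It is either the state at waking or a recollection of a time when the subject was asleep, and the protocol does not say which is wanted. Timing matters because section 5.4.1.1 describes swelling as worsening through the first 24 hours. An unrescued placebo attack read late may therefore look worse than it did at 4 hours, while an attack rescued after 4 hours may look better.

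At stake are the endpoint used for the p < 0.001 test and the two other 4-hour responses. The first permitted look has 12 subjects, which is 24 active and 12 placebo attacks, so a few misdated readings could move the estimate.

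**Working it through.** The plan gives no figure to reproduce: it states neither how often 4 hours falls in sleep nor how long the delay is, and section 13.1 says the sample size has no statistical basis. The sizes below rest on stated assumptions.

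**1. What the entry contains.** Sections 7.1.2 and 11.2.2.1.2 introduce the timed questionnaire and the VAS together, then give the sleep rule for those same times. Including the VAS is the natural reading. Taken literally, though, the rule names only the diary questionnaire, which 11.2.2.1 lists apart from the VAS. The two readings give:
- VAS included: a late VAS sits in the 4-hour slot.
- VAS not included: the 4-hour VAS is missing, with no handling rule in the protocol, and the global-assessment and severity items are still late.

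**2. How late the entry is.** Set bedtime at hour 0, waking at hour S and dosing at hour d (negative if before bed). The subject is asleep at 4 hours post-dose when −4 ≤ d ≤ S − 4, and the waking entry is made S − d hours post-dose. It therefore ranges from just over 4 to S + 4 hours. If d is spread evenly, the share made at 6 hours or later is (S − 2)/S. The share of waking-hour doses given in the last 4 hours before bed is 4/(24 − S).

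| Sleep S (assumed) | Latest entry, S + 4 | Entry if dosed before bed | Share at 6 h or later | Waking-hour doses in last 4 h |
|---|---|---|---|---|
| 6 h | 10 h | 6 to 10 h | 67% | 22% |
| 7 h | 11 h | 7 to 11 h | 71% | 24% |
| 8 h | 12 h | 8 to 12 h | 75% | 25% |
| 9 h | 13 h | 9 to 13 h | 78% | 27% |

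Entries shortly after 4 hours arise when dosing follows a night-time waking. Section 11.2.2.1.2 allows this for abdominal attacks with onset in sleep.

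**3. How many attacks.** Part 1 has at most 36 × 3 = 108 treated attacks (72 active, 36 placebo). At 5%, 10% and 25% affected, that is 5.4, 10.8 and 27. At the 12-subject look (36 attacks) it is 1.8, 3.6 and 9. The last column of the table is an upper guide, since it assumes evenly spread dosing and that every such subject is asleep at 4 hours.

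**4. Direction.** Assume true 4-hour response rates of 0.70 active and 0.40 placebo (difference 0.30), with 25% late entries.
- Late entries better (0.80 active, 0.70 placebo, for example after later rescue): active 0.75 × 0.70 + 0.25 × 0.80 = 0.725; placebo 0.75 × 0.40 + 0.25 × 0.70 = 0.475; difference 0.25.
- Untreated placebo attacks worse (0.70 active, 0.25 placebo): active 0.70; placebo 0.75 × 0.40 + 0.25 × 0.25 = 0.3625; difference about 0.34.

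At 10% late entries the two differences are 0.28 and 0.315.

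**5. Rescue.** The failure rule looks only at use before 4 hours. A subject who wakes after 4 hours, takes standard of care and then completes the entry is not a failure under that rule, even though the reading follows rescue.

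**The case against.** The strongest reply is that the rules for this study's analysis cannot be seen. Section 13.3 defers time points and missing data to a SAP, and only the study-302 SAP was supplied. Windows could still be set there before database lock. This stands: what can be said is that the protocol text permits late readings to enter, not that they will be analysed as 4-hour values. The diary form was not supplied either and may already capture clock times.

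The trial is exploratory, the p < 0.001 analysis is optional, and the sleep rule applies blind and within subject to both treatments. That lowers the stakes. It does not guarantee that the errors cancel, because sleep after dosing may depend on response.

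Three stronger inferences are tempting, and the documents do not support them.
- **That the entries fall 6 to 12 hours post-dose.** No such range is stated. It depends on assumed sleep, and the lower end is just over 4 hours.
- **That about a quarter of attacks are affected.** The exception covers only a subject actually asleep during usual sleeping hours. Otherwise the investigator calls if not contacted within 5 hours. The investigator must also confirm a setting suitable for the timed diary.
- **That a subject could wake at 5 hours, take rescue, sleep again and make the entry at 9 hours within the rules.** The entry and a call to the investigator are both due on waking. The gap that remains is rescue taken after waking but just before the entry, which is narrow.

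**Conclusion.** The point holds in a limited form and should be fixed. Followed as written, the protocol puts an entry of unlimited lateness into the 4-hour slot. It sets no window, and its failure rule does not reach standard of care taken between 4 hours and that entry. Sections 7.1.2 and 11.2.2.1.2 also disagree on which entries are due on waking.

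The size rests on assumptions: a delay of up to about 10 to 13 hours if sleep lasts 6 to 9 hours, and about 5, 11 or 27 of at most 108 Part 1 attacks at an assumed 5%, 10% or 25%. A reader might infer that the rule favours the drug. The documents do not support that, since the contrast can move either way. If the VAS is not part of the waking entry, the fault in the lead endpoint is missing data rather than late data, and the other two 4-hour endpoints are still affected. No sample-size figure changes, because none is stated.

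**What to change.** - Reconcile 7.1.2 with 11.2.2.1.2. State whether the VAS is due on waking, and whether the subject rates the present state or recalls 4 hours.
- Record the actual clock time of each entry, if the diary does not already do so.
- In 13.3.3 and the study-202 SAP, before any unblinded look, define a 4-hour analysis window and assign waking entries outside it to their actual time.
- For analysis only, score standard of care taken at any time before the reading used as the 4-hour value as failure. This leaves the subject's access to treatment unchanged.
- Report two sensitivity analyses, with slept-through 4-hour points counted as non-response in one and excluded in the other. Exclusion alone could bias the contrast if sleep depends on response.

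The cost is protocol and SAP wording, possibly one diary field, and slightly fewer attacks evaluable at 4 hours.
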